12.4 Evaluation and Documentation of Adverse Events and Device Deficiencies

Investigators are required to evaluate and document in the subject's medical records all adverse events and device deficiencies (per the definitions in Table 1: Adverse Event and Device Deficiency Definitions) observed in study subjects from the time they are enrolled until they are exited from the study.

12.5 Adverse Event and Device Deficiency Classification

All AEs and DDs will be reviewed by a Medtronic representative. AEs will be classified according to the definitions provided (Table 2: Adverse Event Classification Responsibilities).

Upon receipt of an AE, a Medtronic representative will review the AE/DD for completeness and accuracy and when necessary will request clarification and/or additional information from the Investigator. Medtronic will utilize MedDRA for Regulatory Activities, to assign a MedDRA term for each AE based on the information provided by the investigator.

AEs and DDs will be classified according to the standard definitions as outlined in the table below:

MDT17051PDS Version 4.0 Page 36 of 56

Table 2: Adverse Event Classification Responsibilities

What is classified?	Who classifies?	Classification Parameters
Relatedness	Investigator	Study Device, Study Procedure
Relateuriess	Sponsor	Study Device, Study Procedure
Seriousness	Investigator	SAE, DD with SADE potential
Seriousness	Sponsor	SAE, DD with SADE potential
Investigator Diagnosis		Based on presenting signs and symptoms and other supporting data
	Sponsor	MedDRA term assigned based on the data provided by Investigator
Death Classification	Investigator	Sudden Cardiac, Non-sudden Cardiac, Non-Cardiac, Unknown

Severity will be defined according to the following criteria:

Mild	Awareness of event, but easily tolerated
Moderate	Discomfort enough to cause some interference with activities of daily living (ADL)
Severe	Incapacitating, with an inability to perform ADL

An AE can be classified as severe and not deemed an SAE. Similarly, an SAE is not automatically severe in nature. These assessments are made by the site Principal Investigator.

12.5.1 Adverse Event Relationship Classifications

Causality assessments define the relationship between the use of the medical device (including the medical-surgical procedure) and the occurrence of each adverse event. The presence of confounding factors, such as concomitant medication/treatment, the natural history of the underlying disease, other concurrent illness or risk factors shall also be considered.

Each AE will be classified according to five different levels of causality for procedure and device. The sponsor and the investigator(s) will use the following definitions to assess the relationship of the adverse event to the investigational medical device and procedures:

Not related: relationship to the device or procedures can be excluded when:

- 1. the event is not a known side effect of the product category the device belongs to or of similar devices and procedures
- 2. the event has no temporal relationship with the use of the device or the procedures;
- 3. the serious event does not follow a known response pattern to the medical device (if the response pattern is previously known) and is biologically implausible;
- 4. the discontinuation of medical device application or the reduction of the level of activation/exposure when clinically feasible and reintroduction of its use (or increase of the level of activation/exposure), do not impact on the serious event;

MDT17051PDS Version 4.0 Page 37 of 56

- 5. the event involves a body-site or an organ not expected to be affected by the device or procedure;
- 6. the serious event can be attributed to another cause (e.g., an underlying or concurrent illness/clinical condition, an effect of another device, drug, treatment or other riskfactors);
- 7. the event does not depend on a false result given by the device used for diagnosis, when applicable;
- 8. harms to the subject are not clearly due to use error;
- 9. In order to establish the non-relatedness, not all the criteria listed above might be met at the same time, depending on the type of device/procedures and the serious event.

Unlikely: the relationship with the use of the device seems not relevant and/or the event can be reasonably explained by another cause, but additional information may be obtained.

Possible: the relationship with the use of the device is weak but cannot be ruled out completely. Alternative causes are also possible (e.g., an underlying or concurrent illness/ clinical condition or/and an effect of another device, drug or treatment). Cases where relatedness cannot be assessed, or no information has been obtained should also be classified as possible.

Probable: the relationship with the use of the device seems relevant and/or the event cannot be reasonably explained by another cause, but additional information may be obtained.

Causal relationship: the serious event is associated with the device or with procedures beyond reasonable doubt when:

- 1. the event is a known side effect of the product category the device belongs to or of similar devices and procedures;
- 2. the event has a temporal relationship with device use/application or procedures;
- 3. the event involves a body-site or organ that
 - a. the device or procedures are applied to;
 - b. the device or procedures have an effect on;
- 4. the serious event follows a known response pattern to the medical device (if the response pattern is previously known);
- the discontinuation of medical device application (or reduction of the level of activation/exposure) and reintroduction of its use (or increase of the level of activation/exposure), impact on the serious event (when clinically feasible);
- 6. other possible causes (e.g., an underlying or concurrent illness/ clinical condition or/and an effect of another device, drug or treatment) have been adequately ruled out;
- 7. harm to the subject is due to error in use;
- 8. the event depends on a false result given by the device used for diagnosis, when applicable;

MDT17051PDS Version 4.0 Page 38 of 56

9. In order to establish the relatedness, not all the criteria listed above might be met at the same time, depending on the type of device/procedures and the serious event.

The Sponsor and the Investigator(s) will distinguish between the adverse events related to the device and those related to the procedures (any procedure specific to the clinical investigation). An adverse event can be related both to procedures and the device. Complications of procedures are considered not related if the said procedures would have been applied to the subjects also in the absence of device use/application.

In some cases, the event may be not adequately assessed because information is insufficient or contradictory and/or the data cannot be verified or supplemented. The sponsor and the Investigator(s) will make the maximum effort to define and categorize the event and avoid these situations.

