9.4 Exclusion Criteria

Pre-Operative Exclusion Criteria

- 1. BMI > 45
- 2. Subject is undergoing emergency surgery
- 3. Subject is pregnant or planning to become pregnant during study participation period
- 4. Subject is unable or unwilling to comply with the study requirements or follow-up schedule
- 5. Subject has comorbidities which, in the opinion of the Investigator, will not be appropriate for the study or the subject has an estimated life expectancy of less than 6 months
- 6. The subject has participated in another investigational drug or device research study within 30 *Medtronic Business Restricted*

MDT17051PDS Version 4.0 Page 23 of 56

days of enrollment

7. Subject has a parastomal hernia

Intra-operative Exclusion Criteria

- 1. Subject's hernia repair is in a contaminated or infected site as assessed by the Investigator (Exclude CDC wound class 2-4; See Section 17.3)
- 2. Subject is undergoing "bridging" repair technique with the mesh placed in an "inlay" position
- 3. Surgeon is unable to completely remove existing mesh from prior surgery
- 4. Surgeon overlays 2 meshes
- 5. Subject receives any mesh other than Parietene™ DS composite mesh

MDT17051PDS Version 4.0

Page 24 of 56

10. Study Procedures

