10.4 Operative (Day 0)

The Study Investigator(s) should perform the elective surgical procedure according to the appropriate standard procedures and practices at the institution using Parietene™ DS Composite Mesh by Open or Laparoscopic approach with intra-peritoneal positioning. During the procedure, every effort should be made to close the defect and Parietene™ DS Composite Mesh used according to the instructions for use (Section 17.4 and 7.5). For study purpose, it is recommended a minimum of 5 cm mesh overlap beyond the edges of the defect and barbed sutures may be used for mesh fixation only if these sutures are claiming such indication. Additionally, the following procedures and assessments will be performed:

- Eligibility Criteria (Intra-operative criteria)
- Serum or urine pregnancy test for females of child-bearing potential unless the subject is surgically sterile or postmenopausal for at least 2 years (reconfirmed as necessary)
- Hernia defect description
- Recurrence history if applicable
- Date of surgery, Operative time (from time of skin incision to closure)
- Conditions of Anesthesia / ASA grade
- Intraoperative wound contamination class (CDC classification, Section 17.3: AppendixC)
- Indication for ventral hernia surgery
- Type of access, defect closure and surgical technique approach
- Mesh size, mesh shape, lot number, positioning, and type of fixation
- Antibiotic prophylaxis
- Area of mesh overlap
- Adverse events assessment
- Surgeon satisfaction questionnaire

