14.1 Statistical Test Methods & Analysis Populations

Statistical analysis consists mainly of a descriptive analysis, and will be performed on:

- the Full Analysis Set (FAS, including any subject enrolled and receiving study device) representing the primary analysis population,
- the Per Protocol Analysis Set [PPAS, a subset of the FAS of subjects who meet the primary endpoint (12-month assessment) and who did not deviate (major) from the protocol], as confirmatory analysis and,
- the Safety Analysis Set (any subject with skin incision including those who are 'screen failure during surgery') for safety and efficacy analysis

Continuous variables will be summarized using counts, means, standard deviations, medians, minimum and maximum. Categorical variables will be summarized using frequencies and percentages.

Time to events analyses using Kaplan Meier estimates and curve will be performed for time to recurrence or to adverse event occurrence

Changes to the planned statistical analysis as defined in the protocol will be documented in the statistical analysis plan and clinical study report.

Statistical analysis will be performed using SAS version 9.4 and Minitab® Version 15.0.

MDT17051PDS Version 4.0 Page 41 of 56

For the purposes of study analysis and statistics adverse event will be defined as procedure related adverse events and adverse device effects.

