14.2 Interim Analysis

Preliminary analysis will be conducted in the study when 30 enrolled subjects complete the 3-month follow-up time-point. The objective is to confirm safety of the product at 3 months. This 3-month time-point is consistent with the wound healing period and the Parietene™ DS Composite Mesh film degradation profile (completely degraded by bulk hydrolysis in less than 15 weeks). This interim analysis is driven by regulatory needs, to support CE marking submission.

Through analysis of clinical data available on a predicate device (Proceed™ surgical mesh) and similar Medtronic composite meshes (Parietene™ Composite Mesh, Parietex™ Composite Mesh) used in ventral hernia repair (primary and incisional) by open or laparoscopic approach assessed during short-term post-surgery report the following adverse event rates:

- 10.6% on the equivalent, Proceed™ surgical mesh used in laparoscopic ventral hernia repair at 3-6 weeks follow-up (9),
- 14.3% on Parietene™ Composite mesh used in laparoscopic ventral hernia repair at 10 weeks follow-up (range 6-25 weeks) (10),
- To 25%, on Parietex™ Composite mesh used in laparoscopic and open ventral hernia repair after
 2 months follow-up with a population of 30 subjects (11), we obtain the following binomial probabilities to observe one or more event(s):

[figure not shown]
Based on these studies, adverse event rates were estimated to range between 11% and 25% and used to generate binomial probabilities to observe at least 1 or 2 AEs with a sample size of 30 subjects as shown in the table below.

N=30 subjects	Hypothetic procedure related adverse event rate						
prob. to observe:	11%	12%	14%	17%	20%	25%	
≥ 1 AE	97.0%	97.8%	98.9%	99.6%	99.9%	100.0%	
≥ 2 AEs	85.7%	89.0%	93.6%	97.3%	98.9%	99.8%	

With an N=30 of enrolled and evaluable subjects at the time of interim analysis, and assuming an 11% adverse event rate, there is a 97% probability to observe at least 1 adverse event and an 85.7% probability to observe at least 2 adverse events. In addition, the probability to observe adverse events increases as the adverse event rate increases to a maximum of 100% and 99.8% for observation 1 and 2 adverse events respectively at an adverse event rate of 25%.

An additional interim analysis is planned to occur for completed 12-month follow-up visit data.

MDT17051PDS Version 4.0 Page 42 of 56

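### The closing rule of Protocol 12.5.1 names no causality axis and, read literally, codes complications of the index hernia repair as not procedure-related, against the protocol's own axes and the interim safety outputs

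*Protocol*

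**What the plan says.** **The rule.** The last full paragraph on causality in Protocol 12.5.1 asks sponsor and investigator to separate device-related events from "those related to the procedures (any procedure specific to the clinical investigation"). It then adds: "Complications of procedures are considered not related if the said procedures would have been applied to the subjects also in the absence of device" use. Neither sentence says which axis the words *not related* refer to.

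**The rest of the causality text.** The same section opens by defining causality as "the relationship between the use of the medical device (including the medical-surgical procedure) and the occurrence of each adverse event", and it requires a five-level grade for procedure and for device. Table 2 in Protocol 12.5 gives both investigator and sponsor the parameters "Study Device, Study Procedure". The operative visit (10.4) sits in the chapter headed "10. Study Procedures". No passage defines the study procedure.

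**The operation.** Inclusion criterion 3 (Protocol 9.3) requires elective ventral hernia repair with intraperitoneal mesh and does not name the study mesh. Protocol 4.1 describes mesh repair as standard of care. Protocol 10.4 says: "The Study Investigator(s) should perform the elective surgical procedure according to the appropriate standard procedures and practices at the institution"; the sentence goes on to specify the study mesh in an intraperitoneal position.

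**The analysis.** Protocol 14.1 states: "For the purposes of study analysis and statistics adverse event will be defined as procedure related adverse events and adverse device effects". The planning table for the first interim (Protocol 14.2, SAP 7.8.1) is headed "Hypothetic procedure related adverse event rate". The SAP 7.8.1 outputs are incidences and listings of AEs and SAEs related to the procedure, the device or both, up to 3 months. SAP 7.10 reports AE incidence overall and by relation to the procedure.

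**The concern.** An assessor can reason as follows. This patient was having an elective mesh repair in any case, so the operation would have taken place without this device, so a complication of the operation is not related. Nothing in the closing sentence stops that reasoning from being applied to the procedure axis, and the restriction to investigation-specific procedures encourages it.

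Complications of the repair would then leave the category that the first interim is built to count. That interim is meant to confirm 3-month safety and support the CE submission, and any error of this kind makes the reported rate lower. The relation-to-procedure breakdown in SAP 7.10 has the same exposure. Because Protocol 14.1 defines the analysed adverse event by relatedness, the overall incidence in SAP 7.10 may be affected as well.

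**Working it through.** **1. The passages side by side**

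| Place | Is the index repair inside procedure-relatedness? |
|---|---|
| Protocol 12.5.1, opening | Yes: the surgical procedure is part of the causality assessment |
| Protocol 12.5, Table 2 | Implied: a separate procedure rating by two assessors |
| Protocol chapter 10 heading and 10.4 | Implied: the operation is listed among study procedures |
| Protocol 12.1 | Weak support: some post-operative events are labelled procedure related, but only to make them conditionally non-reportable |
| Protocol 14.1, 14.2; SAP 7.8.1 | Needed: procedure-related events are what is counted |
| Protocol 12.5.1, close | No, if read literally with Protocol 9.3 and 4.1 |

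**2. The plan's own figures.** With n = 30 and event rate p, P(≥1) = 1 − (1−p)^30 and P(≥2) = P(≥1) − 30p(1−p)^29.
- p = 11%: 1 − 0.89^30 = 97.0%; subtracting 30 × 0.11 × 0.89^29 gives 85.7%.
- p = 25%: 99.98% (printed as 100.0%) and 99.8%.

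All 12 printed cells reproduce to within 0.1 percentage point. The table is sound provided the events it counts are coded as related.

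**3. Effect per subject.** One subject is 1/30 = 3.3 percentage points. Expected subjects with an event are 30 × 0.11 = 3.3 and 30 × 0.25 = 7.5. SAP 7.2 plans 95% intervals for categorical variables but names no method; the exact Clopper-Pearson interval is assumed here.

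| Near planning rate | Subjects counted | Incidence (95% CI) |
|---|---|---|
| 11% | 3/30 | 10.0% (2.1–26.5) |
| 11%, one subject recoded | 2/30 | 6.7% (0.8–22.1) |
| 11%, two subjects recoded | 1/30 | 3.3% (0.1–17.2) |
| 25% | 8/30 | 26.7% (12.3–45.9) |
| 25%, one subject recoded | 7/30 | 23.3% (9.9–42.3) |

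**4. Sensitivity to the share recoded.** The documents give no share. Let f be the assumed share of subjects with a related event who drop out of the count, so that the counted rate is p(1−f).

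| f (assumed) | p = 11%: P(≥1) / P(≥2) | p = 25%: P(≥1) / P(≥2) |
|---|---|---|
| 0 | 97.0% / 85.7% | 100.0% / 99.8% |
| 25% | 92.4% / 72.1% | 99.8% / 98.4% |
| 50% | 81.7% / 49.7% | 98.2% / 90.4% |
| 75% | 56.7% / 19.9% | 85.6% / 56.7% |
| 90% | 28.2% / 4.3% | 53.2% / 17.2% |

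These rows show direction and scale only; nothing in the documents favours any value of f above zero.

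**The case against.** **The document as a whole points the other way.** Protocol 10.4 describes an operation with the study mesh and adds study-specific recommendations, so it is arguable that this procedure would not occur without the device. Apart from surgery, the schedule in Protocol 10.1 consists mostly of questionnaires, tests, history and follow-up assessments. A reading that leaves out the repair nearly empties the procedure axis. This stands: the two readings are not equally supported. It does not settle the matter, because the closing sentence is an explicit rule, and the text leaves open whether its device means this mesh or any mesh.

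**Several safeguards work against under-counting.** A sponsor representative reviews every AE, and the sponsor also classifies relatedness (Protocol 12.5). For the interim, differing assessments are reconciled to the most conservative one (14.2), so one assessor using the broad reading keeps the event in. Events may also stay in as adverse device effects, through attribution to both procedure and device, or through the default to *possible* when relatedness cannot be assessed. All of this limits the effect. It does not remove it, because all assessors work from the same sentence. The Independent Medical Monitor (13.1) reviews SAEs and events potentially related to the procedure or product, so a non-serious event already coded unrelated may not reach that review.

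**Stronger readings the documents do not support.** A reader might infer that complications are lost from the study. They are not: Protocol 12.6 records all AEs whatever their relatedness. A reader might infer that site-to-site differences in coding will pass straight into the results; sponsor review and reconciliation stand in between. A reader might also take one of the assumed shares above as a forecast; the documents give no basis for that.

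**Conclusion.** The conflict is real and should be corrected. A stated rule, applied as written, gives a safety count that the rest of the protocol and the SAP do not intend. The consequence is a possible downward bias of unknown size in descriptive procedure-related AE rates: 3.3 percentage points for each affected subject at the first interim, and an undetermined amount in the SAP 7.10 breakdown by relation to the procedure. The overall incidence in SAP 7.10 is exposed only if the Protocol 14.1 definition is applied to it; the SAP's own glossary defines an AE regardless of relatedness, so that is a possibility and no more.

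The primary endpoint, hernia recurrence, does not use relatedness. The secondary safety endpoints are based on adverse device effects and are touched only if the sentence is applied to the device axis. No planned decision changes, because no test or threshold in either document uses the count; the wide overlap of the intervals is not the reason.

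The conclusion rests on the literal reading being open to an assessor, not on evidence that anyone has used it.

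**What to change.** Reconcile the passages in three steps.

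1. In Protocol 12.5.1, state that the index ventral hernia repair is a study procedure for the procedure-relatedness axis, and that the closing sentence covers only procedures other than the index repair.
2. Use the same definition in SAP 7.8.1 and 7.10, and say in 7.10 whether the overall incidence covers all recorded AEs or only those in the Protocol 14.1 definition.
3. Before analysis, have the existing assessors (investigator, sponsor and, where applicable, the Medical Monitor) confirm procedure relatedness under that definition for all peri-operative AEs, whatever their present code.

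Confining the closing sentence to the device axis may look simpler but should be avoided. Complications of the repair could then be coded as not device-related on the ground that the repair would have happened anyway. That could lower ADE incidence and alter time to ADE, which are named secondary endpoints (Protocol 5.2.2, SAP 7.9).

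The cost is a short clarification in each document and a small coding check. Visits and sample size do not change. The downside is that reported procedure-related AE rates may rise.

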12.6 Adverse Event and Device Deficiency Reporting Requirements

Investigators are obligated to report applicable adverse events to the study sponsor and in accordance with reporting requirements of their IRB.

Events will be reviewed by the sponsor to determine any reporting obligations to IRBs and regulatory authorities.

SAEs need to be reported to the sponsor within 24 hours of becoming aware.

Assessment of the occurrence of an AE will be based on changes in the subject's physical examination, laboratory results and/or signs and symptoms. Adverse events will be monitored until a subject completes the study, or unless the Investigator determines the event is related to the device, in which case they will be monitored until resolution if possible. Medical care will be provided, as defined in the informed consent, for any AE related to study participation. Adverse events will be collected on an AE eCRF and applicable source documentation. To the extent possible, the event to be recorded and reported is the event diagnosis as opposed to event symptoms (e.g., fever, chills, nausea and vomiting in the presence of a clinically diagnosed infection is to be reported as infection only). For subjects who are screen failure during surgery (Section 10.12.2.2) AEs will be recorded at time of enrollment until discharge. For other subjects, AEs occurring at time of enrollment and up to and including 24 months follow-up will be recorded.

The following should not be considered an AE:

- A condition requiring a preplanned procedure unless the condition worsened since screening
- A pre-existing condition found at the time of screening, unless the condition has worsened since enrollment.

All responses to the above events that require treatment beyond the institution's standard procedures must be reported.

MDT17051PDS Version 4.0 Page 39 of 56

All AEs observed during the course of this study, regardless of severity, seriousness, or relationship to the device and procedure will be recorded on the appropriate AE eCRF.

